3.3.2 Total Number of Study Sites/Total Number of Subjects Projected

The study will only be conducted at Children's Hospital of Philadelphia.

It is expected that approximately 60 subjects will be enrolled to produce at least 45 evaluable subjects.

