adolescents with AN. To determine optimal dose, we will model change across the 15 sessions using latent growth curve modeling (LGCM). LGCM will allow us to analyze individual and average trajectory and model linear and quadratic trend. We will visually assess for the point (dose) at which there is a significant decrease in the *rate* of improvement (quadratic). Parameter estimation will employ Maximum Likelihood (ML) estimation.^{93,94} We will evaluate model fit using chi-square (χ^2), Comparative Fit Index (CFI), Standardized Root Mean Squared Residual (SRMR), and Root Mean Squared Error of Approximation (RMSEA).⁹⁵ The following values are indicative of acceptable fit between the model and the observed data variance/covariance matrixes: CFI, SRMR, and RMSEA, $< .95$, $< .80$, and $< .05$, respectively. We will assess and compare different models using BIC and novel criteria such as Scaled Unit Information Prior BIC.^{96,97} Examining standardized model residuals in addition to global fit indices (GFI) permits us to identify model misspecification even if GFI values suggest adequate fit.⁹⁵

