6.4 Sample Size and Power

Power analysis Aim 1. In the initial phase of the proposed project (R61), our sample size estimation is based on a mixed MANCOVA design with two repeated measures from baseline to end-of-treatment (EOT; within subjects component) and three groups (CRT_P, CRT_A, and FBT; between subjects component). Based on a review of the literature, we are powering for a medium effect size. Our effect size estimate is Cohen's f statistic.⁹⁸ This effect size estimate is a ratio of variation explained to that unexplained by the model (treatment groups), and is expressed as

follows: $f = \sqrt{\frac{\eta^2}{(1-\eta^2)}}$, where $\eta^2 = \frac{\sigma_{model}^2}{\sigma_{Total}^2}$; proportion of variability due to the model.^{99,100}

Heuristics for small, medium, and large effect sizes are .1, .25, and .4, respectively. We selected an alpha of 0.15, given the nature of the study and the difficulty in recruiting participants from a low prevalence condition. Alpha of 0.15 is essential to provide adequate power for this study.⁹¹ As any analysis powered for a medium effect will also be powered for a large effect, we only highlight the expected medium effect. For all analyses, we specified an $\alpha=0.15$, two time points, and a correlation between measures of .3 (based on unpublished data). The anticipated N accounts for dropouts (i.e., number enrolled will be higher).

Power analysis Aim 2. Using Mplus 7.2,⁹⁴ we conducted a LGCM Monte Carlo simulation with 1000 replications^{94,101-103} to determine power to identify CRT_{P/A} dosage based on a half standard

deviation increase (rate of change; slope) from baseline (effect size) above FBT. With 15 participants in 3 groups across 5 time points, parameter and standard error bias were $\leq 5\%$, confidence interval coverage $\geq 90\%$, and power = 0.59.

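### Aim 2 fits growth curves by maximum likelihood with 15 participants per arm and no small-sample correction, so its tests and intervals are modestly too optimistic and the stated power of 0.59 may be too.

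*Combined protocol and SAP*

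**What the plan says.** Aim 2 is listed among the primary aims (Section 2.1). Section 6.1 plans latent growth curve models: "LGCM will allow us to analyze individual and average trajectory and model linear and quadratic trend". On estimation it says "Parameter estimation will employ Maximum Likelihood (ML) estimation". Fit is to be judged by chi-square, CFI, SRMR, RMSEA and standardized residuals, and models compared by BIC-type criteria. The dose is then found from the curve: "We will visually assess for the point (dose) at which there is a significant decrease in the" rate of improvement.

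Section 6.4 supports this with a simulation: "we conducted a LGCM Monte Carlo simulation with 1000 replications", for a half-standard-"deviation increase (rate of change; slope) from baseline (effect size) above FBT". The setting is "With 15 participants in 3 groups across 5 time points", which agrees with Section 3.3.2: "It is expected that approximately 60 subjects will be enrolled to produce at least 45 evaluable subjects". The results given are parameter and standard-error bias of at most 5%, then "confidence interval coverage $\geq 90\%$, and power = 0.59".

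Neither section names REML, t-based or Kenward-Roger inference, bootstrap or any other small-sample method for Aim 2. Neither gives the interval level, the sidedness, the tested contrast, the growth variances, or whether the arms share a covariance matrix. An alpha of 0.15 appears in the Aim 1 text and in the Aim 1 power paragraph, where it is tied to two time points. It is not restated for Aim 2.

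**The concern.** ML variance estimates divide by the number of people rather than by that number minus the fitted group means, so standard errors come out too small. Growth-model software then usually refers the estimate to the normal distribution rather than to t. In large samples neither matters. With 15 people per arm both push the same way, towards too many significant results and intervals that are too narrow.

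At stake are the slope and quadratic terms that describe how flexibility changes over the CRT sessions, the differences from FBT, and the reading of the 0.59. That power is already low, and if it was computed with the same optimistic error bars the honest figure is lower still.

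**Working it through.** **Inputs from the documents.** 15 per arm, three arms, five time points, standard-error bias at most 5%, coverage at least 90%, power 0.59 (Section 6.4); ML estimation (Section 6.1).

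**Assumed.** Normal critical values. Nominal error of 5% or 15%, both shown because Aim 2 states neither. Complete data.

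**Can the 0.59 be reproduced?** No, because the variances, alpha and contrast are missing. A plain two-group comparison at d = 0.5 with two-sided alpha 0.05 gives 0.277 (15 v 15) and 0.352 (15 v 30). At two-sided 0.15 it gives 0.472 and 0.556. Other one-sided and one-group variants run from 0.39 to 0.82, and none falls within 2 points of 0.59. This does not show that 0.59 is wrong.

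**Closed form for the error rate.** For a contrast of person-level slopes in complete data, the ML standard error is the unbiased one times sqrt(df/N). The true error is therefore 2 × P(t_df > z × sqrt(df/N)). In all three cases below sqrt(df/N) = sqrt(14/15) = 0.966, a standard-error shortfall of about 3.4%, which is inside the plan's 5%. The effective cut-off is 1.960 × 0.966 = 1.893 at nominal 5%, and 1.440 × 0.966 = 1.391 at nominal 15%.

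| Term | N, df | True error at nominal 5% | 95% coverage | True error at nominal 15% |
|---|---|---|---|---|
| Single-arm mean | 15, 14 | 7.9% | 92.1% | 18.6% |
| Contrast, two arms | 30, 28 | 6.9% | 93.1% | 17.5% |
| Contrast, three arms pooled | 45, 42 | 6.5% | 93.5% | 17.2% |

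**Simulated growth-model fits.** ML fits with 1500 replications per setting, 15 per arm and five times (equally spaced, or weeks 0/4/9/13/18), with linear or linear plus quadratic trends. Assumed variances: intercept 0.5, slope 0.1, quadratic 0.01, residual 0.5. Results for arm differences at nominal 95%:

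| Covariance structure | Coverage | Standard-error bias |
|---|---|---|
| Equal residual variances (pooled or separate arms) | 92.5-94.1% | about -2% to -5% |
| Free residual variances, pooled covariance | 92.6-93.0% | -6% to -8% |
| Free residual variances, arm-specific covariance | 89.0-90.3% | -12.5% to -15% |

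In the last row, single-arm terms cover 87.7-89.4%. Across all settings, nominal 85% intervals for arm differences cover about 77-84%. Only the first row is close to the plan's reported standard-error bias.

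**Effect on the 0.59, if it came from an ML test with normal critical values.** Find the noncentrality that gives 0.59 at the effective cut-off, then recompute with the correct t critical value.

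| Term | Nominal 5%: noncentrality, t cut-off, power | Nominal 15%: noncentrality, t cut-off, power |
|---|---|---|
| Pooled contrast, 42 df | 2.11, 2.018, 0.54 | 1.61, 1.466, 0.56 |
| Two-arm contrast, 28 df | 2.11, 2.048, 0.53 | 1.61, 1.480, 0.555 |
| Single-arm mean, 14 df | 2.10, 2.145, 0.50 | 1.60, 1.523, 0.54 |

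**The case against.** The best reply is that the plan has already tested this. Its own simulation of 15 per group reports standard-error bias of at most 5% and coverage of at least 90%, which is where modest undercoverage would show. That stands, and it bounds the problem. A reader might infer that the intervals cover as little as 88%. The checks reach 88-90% only with arm-specific covariances and free residual variances, where standard-error bias is -12% or worse, and that conflicts with Section 6.4 for the setup simulated there. It remains possible for the actual analysis, because the covariance structure is not stated. Nor does the 90% bound show that the error rate doubles: it is a lower limit, not the coverage achieved. It also carries no nominal level, and no type I error is given.

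A reader might also take it as fact that the 0.59 comes from a test that rejects too often. The documents do not define that test, so this is conditional on ML with normal critical values.

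A third reply is that little turns on it. The dose is read visually, and Section 6.1 links the Go/No-Go decision to the Aim 1 steps. This also stands: neither the dose rule nor the Go/No-Go is shown to change. If alpha 0.15 was meant for Aim 2, a true error of about 17-19% is a small excess over a rate already accepted as high.

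Lastly, replacing ML outright would discard the fit checks planned in Section 6.1. That is right, and the change below keeps them.

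**Conclusion.** The concern holds as a modest, cheaply corrected weakness in a primary aim. ML with normal-based inference at 15 per arm undercovers in every setting tried. For a setup consistent with Section 6.4, 95% intervals would cover about 92-94%, with 90-94% supportable. True error is about 6.5-7% for arm contrasts and 8% for a single-arm term at nominal 5%, and about 17-19% at nominal 15%. If the 0.59 rests on the same inference, power at the true nominal level is about 0.53-0.56 for arm contrasts and 0.50-0.54 for a single-arm term.

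The direction rests on the use of normal critical values without correction, which is usual for these models but not stated. The sizes rest also on complete data and, in the simulated fits, on assumed variances. What is affected is the reported slopes, quadratic terms, intervals and stated power. The change should be made, but the trial's decisions do not hang on it.

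**What to change.** 1. For all Aim 2 tests and intervals, fit the same mean model (same arms, time scores, linear and quadratic terms) as a linear mixed model by REML, with Kenward-Roger standard errors and degrees of freedom.
2. Keep the ML growth curve for chi-square, CFI, SRMR, RMSEA, residual checks and BIC comparisons.
3. State for Aim 2 the alpha and sidedness, the interval level, the contrast tested, and whether covariances and residual variances are shared across arms and times.
4. Rerun the Section 6.4 simulation with this analysis and report power, exact coverage and type I error in place of the lower bound. The rerun should use the waves available for each outcome: Section 3.3.1 lists neuropsychological testing at T1, T3, T4 and T5, which is four waves, while the simulation used five.

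The cost is SAP wording and one rerun. Intervals will be slightly wider and the stated power probably a few points lower. No patients, visits or data are added.

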3.3 Study Duration, Enrollment and Number of Sites

3.3.1 Duration of Study Participation

Total study duration for each participant is approximately 12-14 months. Participants will have 6-12 months of active treatment. If there is a delay in treatment (brief hospitalization or cancelation of an appointment due to weather, illness, etc.) treatment duration may be slightly longer. It is anticipated that all treatment will be complete within 12-14 months of enrollment.

Adolescents and their families will be assessed at five time points:

- T₁: neuropsychological assessment, therapy session, questionnaires, Grocery store (parents), Buffet challenge (adolescent)
- T₂: therapy session, questionnaires
- T₃: neuropsychological assessment, questionnaires
- T₄: neuropsychological assessment, questionnaires, Grocery store (parents), Buffet challenge (adolescent)
- T₅: questionnaires, neuropsychological assessment, Grocery store (parents), Buffet challenge (adolescent)

- T₆: Medical chart review and questionnaires (to be completed online/ mailed to the family, this will take place 3 months post end of primary treatment intervention)
- T₇: Medical chart review and questionnaires (to be completed online/ mailed to the family, this will take place 6 months post end of primary treatment intervention)

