6 STATISTICAL CONSIDERATIONS

6.1 Primary Endpoint

Aim 1: To identify whether or not it more impactful to add a parent or adolescent component of CRT to standard FBT. To assess if CRT engages the target, we will use mixed 3 (treatment) x 2 (time) Multivariate Analysis of Covariance (MANCOVA): one for adolescents, one for mothers, and one for fathers. The covariate for all analyses is total IQ on the WASI. Dependent variables are as follows: Trails Number-Letter Sequencing, Inhibition, Inhibition/Switching, Correct Response Shifting, Category Switching, or Description 1 or 2 and Shift on the BRIEF-2. We will follow these steps:

1. Conduct omnibus MANCOVA and evaluate significance. If not significant, stop and move to next analysis.
2. If the omnibus test is significant, we will conduct individual 2 (treatment) X 2 (time) Analysis of Covariance (ANCOVA) to determine which dependent variable had significant change, with IQ again as the covariate.
3. Each assessment of the target (DV) will be examined. Results will inform the Go/No-Go Decision as described in Table 6.

These three steps will be repeated for adolescents, mothers, and fathers. We will include all three groups in the initial MANCOVA and follow-up with planned comparisons (ANCOVA) of FBT vs the appropriate CRT condition. In all analyses, we will focus on the within and between-group effects, examining interaction effects are not necessary to evaluate the target. As we have chosen measures demonstrated to change with CRT,^{40,87-90} we will maintain $\alpha=0.15$ for each analysis.⁹¹ We do not expect adolescents whose parents receive CRT or parents whose adolescents receive CRT to demonstrate increases in flexibility. However, should the planned ANCOVAs not be significant, we will be able to explore other possible group differences. Additionally, we will explore the relationship between dependent variables via discriminant analysis. These additional methods to examine the data will not factor into the Go/No-Go decision, but will enhance the depth of our understanding of the data and contribute to our understanding of neurocognition in AN.

Aim 2: To determine the dose of CRT needed to lead to a medium effect size. Some research indicates that ≥ 8 sessions of CRT are necessary for improvement in cognitive flexibility with AN.⁹² It is unknown how many sessions will be needed for significant change in parents of

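### Two Aim 2 growth-model fit limits are wrong as printed: the CFI inequality is reversed, and an SRMR limit of .80 excludes almost nothing

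*Combined protocol and SAP*

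**What the plan says.** Section 6.1 specifies one analysis for Aim 2, a latent growth curve model of change across the 15 sessions with linear and quadratic trends. On judging fit it says: "We will evaluate model fit using chi-square (χ^2), Comparative Fit Index (CFI), Standardized Root Mean Squared Residual (SRMR), and Root Mean Squared Error of Approximation". It then introduces its numerical limits with "The following values are indicative of acceptable fit between the model and the observed data variance/covariance matrixes" and lists them as "CFI, SRMR, and RMSEA, $< .95$, $< .80$, and $< .05$, respectively". The limits are therefore values that signal good fit, and each is tied to a named index. No other section restates or corrects them.

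The same paragraph also plans BIC-type comparison of models and inspection of standardized residuals, and the dose is read visually from the curve. For size, section 6.4 describes the Aim 2 power simulation as "With 15 participants in 3 groups across 5 time points".

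**The concern.** CFI and SRMR run in opposite directions: high CFI is good and low SRMR is good. A single less-than sign applied to both cannot be right for both. As printed, the CFI limit treats good fit as unacceptable and poor fit as acceptable. Separately, .80 is very large for an index that is zero at perfect fit and is built from residuals on the correlation scale.

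These are the only numerical fit limits for the only analysis of a primary aim. An analyst who follows them literally would misjudge the model. One who silently replaces them would be choosing fit criteria after seeing the data.

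**Working it through.** The plan has no computed figure to reproduce here. The stated Aim 2 power of 0.59 was not recomputed, because the variance components behind it are not given and this point does not depend on it.

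**Inputs**
- Limits: section 6.1, as quoted above.
- Occasions, T: five in the section 6.4 power statement. Section 3.3.1 lists "T₂: therapy session, questionnaires" with no neuropsychological assessment at that visit, so T is four if the modelled outcome comes from those tests.
- Correlation between occasions, r: section 6.4 uses "a correlation between measures of .3 (based on unpublished data") for Aim 1. Applying .3 to Aim 2 is an assumption, so a range is also shown.
- N: 15 per group × 3 = 45.

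**Step 1. CFI.** CFI = 1 − max(χ²_M − df_M, 0) / max(χ²_M − df_M, χ²_B − df_B, 0), where M is the fitted model and B the zero-covariance baseline. Perfect fit gives 1, and the baseline itself gives 0. This follows from the definition and needs no assumption about the data.

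**Step 2. SRMR of a model with no correlation between occasions.** Take variances reproduced exactly and all true correlations equal to r. Then SRMR = r × √([T(T−1)/2] / [T(T+1)/2]).
- T = 5: r × √(10/15) = .816r. At r = .3 this is .245. For r from .1 to .9 it runs from .082 to .735.
- T = 4: r × √(6/10) = .775r. At r = .3 this is .232. For r from .1 to .9 it runs from .077 to .697.
- Correlation needed to reach .80: .80/.816 = .980 (T = 5); .80/.775 = 1.033, which is impossible (T = 4).
- If T exactly fitted means are also counted, the factors fall to .707 and .655, and .80 is never reached.
- For comparison, a limit of .08 would be passed at r = .098 (T = 5) or .103 (T = 4).

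**Step 3. RMSEA of the same model.** F0 = −ln[(1−r)^(T−1) × (1+(T−1)r)], df = T(T−1)/2, RMSEA = √(F0/df). At r = .3:
- T = 5: F0 = −ln(.2401 × 2.2) = .638; √(.638/10) = .253.
- T = 4: F0 = −ln(.343 × 1.9) = .428; √(.428/6) = .267.

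**Step 4. Set against the printed limits (r = .3)**

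| Model | CFI < .95 | SRMR < .80 | RMSEA < .05 |
|---|---|---|---|
| Perfect fit | 1: outside | 0: inside | 0: inside |
| No correlation between occasions | 0: inside | .245 or .232: inside | .253 or .267: outside |

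**Step 5. Simulation.** The settings, all assumed, were: one group, five occasions, linear growth, intercept variance .3 or .7 with baseline variance 1, slope variance .3, mean change 0.5 SD, and 400 replications per setting. The correct linear model was compared with a wrong intercept-only model.
- N = 500: the printed CFI limit was met by 0% of correct fits and 100% of wrong fits.
- N = 45: it was met by 14–38% of correct fits and 90–95% of wrong fits.
- Every fit, right or wrong, met SRMR < .80 (largest value .324).
- All three printed limits together were met by 0–1.3% of correct fits and 0–1.5% of wrong fits.

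**Step 6. What corrected limits would do.** With CFI ≥ .95, SRMR < .08 (an assumed value) and RMSEA < .05 in the same simulation, the wrong model met all three in 0% of replications. The correct model met them in 99.3–99.5% at N = 500, but in only 6.5–50% at N = 45.

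RMSEA can also be checked from the chi-square distribution. For a correct model with quadratic mean, random intercept and slope, and free residual variances, df is 9 (T = 5) or 4 (T = 4). The limit requires χ² < df × (1 + .0025(N−1)).
- N = 45: 9 × 1.11 = 9.99 or 4 × 1.11 = 4.44, met with probability .649 or .650.
- N = 15 (one group alone): 9 × 1.035 = 9.315 or 4 × 1.035 = 4.14, met with probability .591 or .613.

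**The case against.** The strongest reply is that little depends on these numbers. They are described as indicative. Section 6.1 adds chi-square, BIC-type comparison and residual inspection, the last expressly to find misspecification that global indices miss. RMSEA, printed correctly in the same sentence, excludes the zero-correlation model by a factor of five, so the printed set as a whole does not accept it. No sample size, alpha or power figure changes. All of this stands and limits the weight of the point. What remains is that the set also excludes a perfectly fitting model, so it does not separate good fit from bad.

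A second reply is that the CFI sign may have been misread from the PDF. That cannot be excluded and should be checked. It is not a strong defence: a greater-or-equal sign survives in the same section ("Some research indicates that ≥ 8 sessions of CRT are necessary"), and others survive in section 6.4. A misread sign would also not explain .80.

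Third, the SRMR bound in the working covers one benchmark model. A growth model can also misfit variances and means, which would raise SRMR. That is fair, and it is why the claim is that .80 excludes almost nothing, rather than nothing at all.

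Finally, the small-sample percentages depend on the model fitted. With a random quadratic term at four occasions (df 1), the RMSEA share at N = 45 is about 71% rather than 65%. They serve only as a caution about using any such limits as a gate.

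**Conclusion.** The concern holds as printed. The reversal of the CFI limit follows from the definition alone. The SRMR limit is too loose to be useful: ignoring all correlation between occasions would breach it only at a correlation above .98 with five occasions, and never with four. That result assumes equal correlations and exactly fitted variances. The figures at r = .3 also borrow the Aim 1 correlation.

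The effect on the trial is limited. No section makes these limits an accept-or-reject rule. The Go/No-Go sentence, "Results will inform the Go/No-Go Decision as described in Table 6", belongs to the Aim 1 steps. Table 6 is not in the text available, so whether it uses Aim 2 could not be seen. No harm to the dose conclusion has been shown. The sentence should still be corrected before analysis, because it states fit criteria for a primary aim that mislead if followed literally.

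**What to change.** Check the source page for a misread sign. Then amend the one sentence in section 6.1: state the CFI criterion as at least .95, and have the sponsor confirm and correct the SRMR limit. The printed .80 looks like a slipped decimal for .08, but the documents do not give the intended value, so that is for the sponsor to settle. RMSEA needs no change of direction.

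Keep all three values indicative, alongside the chi-square test, BIC-type comparison and standardized residuals already planned. The cost is one sentence, with no new data and no change to sample size or alpha. The drawback is that at 45 participants, corrected limits will often flag a correctly specified model, so they should not serve as the sole gate.
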